7.8.3 Vital signs

Only descriptive statistics are planned for this section of the report.

A summary table of left ventricular ejection fraction (LVEF) will be produced for the final and minimum on-treatment values along with the corresponding percentage change from baseline. The number of patients with a significant LVEF event will also be presented. A significant event is defined as a decrease of $\geq 20\%$ from baseline that is also below the lower limit of normal of the investigational site (50% will be used if the lower limit of normal is missing).

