| dose: | Starting dose 40 mg daily, escalation to 50 mg/day and/or reduction to 40, 30 then 20 mg according to absence or presence of drug related adverse events. | | |
| Mode of admin. : | Oral | | |

Proprietary confidential information. © 2019 Boehringer Ingelheim International GmbH or one or more of its affiliated companies.

| | | | | | |
|--|---|-------------------------------------|--|--|--|
| Name of company: Boehringer Ingelheim | | Tabulated Trial Protocol | | | |
| Name of finished product: Not applicable | | | | | |
| Name of active ingredient: Afatinib (BIBW 2992) | | | | | |
| Protocol date: 07 Feb 2013 | Trial number: 1200.161 | | Revision date: 03 January 2019 | | |
| Comparator products: Methotrexate | | | | | |
| dose: 40 mg/m ² / week with an option to escalate to 50 mg/m ² / week and/or to reduce to 40, 30 then 20 mg/m ² / week according to drug related adverse events. | | | | | |
| Mode of admin. : Intravenous bolus injection | | | | | |
| Duration of treatment: Both treatment arms: continuous treatment until disease progression confirmed by imaging or adverse events requiring permanent discontinuation from treatment. After primary analysis, duration of treatment may be limited to one year after the last patient randomised. | | | | | |
| Criteria for efficacy and pharmacokinetics: | Primary Endpoint: • Progression free survival (PFS) based on RECIST version 1.1 | | | | |
| | Secondary Endpoints: • Overall survival (OS) • Objective response rate based on RECIST version 1.1 • Health related quality of life (HRQOL) | | | | |
| Pharmacokinetics: Pharmacokinetics of Afatinib (i.e. plasma concentrations) | | | | | |
| Criteria for safety: | Incidence and intensity of adverse events (CTCAE, version 3.0), and changes in safety laboratory parameters, vital signs, ECOG status and ECG. | | | | |
| Statistical methods: | This study will be powered to demonstrate the PFS benefit of Afatinib over methotrexate. The total progression (or death) events needed is 274 to detect a 43% improvement in median PFS (Afatinib 3.0 months vs. methotrexate 2.1 months; hazard ratio=0.70) with one-sided type-I error α =0.025 and 80% power. Overall 330 patients will be randomised. A stratified log-rank test will be used to test PFS. All safety endpoints and Afatinib plasma concentrations will be analysed descriptively. | | | | |

Proprietary confidential information. © 2019 Boehringer Ingelheim International GmbH or one or more of its affiliated companies

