5.2.4.5 Vital signs and body weight

Vital signs (blood pressure and pulse after 5 minutes seated rest), and body weight (without overcoat and shoes) will be recorded at the time points specified in the [Flow Chart](#).

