7.3.3 Safety analyses

Safety analyses will be based on Treated Set, i.e., all patients who receive at least one dose of study medication will be included in the analysis of safety. The safety analysis will be descriptive and exploratory in nature. Adverse events will be graded according to United States NCI CTCAE, Version 3.0 ([R04-0474](#)).

Key safety measures will include:

- the overall incidence and intensity of AEs, as well as relatedness of AEs to treatment and seriousness of AEs
- AEs leading to dose reduction or permanent treatment discontinuation
- gastrointestinal events (vomiting, nausea, diarrhoea)
- skin reactions (rash, acne)
- other serious or significant AEs according to ICH E3
- decreased cardiac left ventricular function (reduction to below LLN and $\geq 20\%$ decrease compared to baseline)
- CTCAE grade 2 with increase by at least one CTCAE grade from baseline, for selected laboratory tests:
- (low values) haemoglobin, leukocytes (total WBC), neutrophils, lymphocytes, platelets, potassium
- (high values) PTT, creatinine, AST, ALT, bilirubin, alkaline phosphatase, proteinuria
- descriptive statistics for change from baseline for all laboratory tests
- causes of death.

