| Rationale for change | | Administrative, should have been removed with previous amendment. |
| Section to be changed | | Flow Charts, footnotes “Tumour imaging...” Section 3.2 Discussion of trial design... Section 5.1.2.1 Tumour imaging Section 6.6.2 Treatment period |
| Description of change | | Imaging intervals can change to follow local site standard (if no standard: every 16 weeks) after database lock for primary analysis. |
| Rationale for change | | Since primary endpoint analysis is conducted at primary analysis, the requirement to continue imaging with the current frequency is not considered to add additional value once the database lock for the primary analysis is complete. Therefore it is considered adequate to allow investigators to follow site standard. |
| Section to be changed | | Flow Charts, footnotes “Only for patients permanently...” Section 3.1 Overall trial design and plan Section 6.2.3.1 End of treatment Section 6.2.3.2 Follow-up visit Section 6.2.3.3 Observational period |
| Description of change | | The requirement to continue imaging for patients who permanently discontinued study medication due to other reasons than disease progression will be removed after database lock for primary analysis. Sentence to address this is added to applicable Flow Chart footnotes and Sections. |
| Rationale for change | | Since primary endpoint analysis is conducted at primary analysis, the requirement to continue imaging for patients who stop study medication without PD is not considered to add additional value once the database lock for the primary analysis is complete. |

Proprietary confidential information. © 2019 Boehringer Ingelheim International GmbH or one or more of its affiliated companies

| | |
|------------------------------|---|
| Section to be changed | Flow Charts, footnotes relating to ECG “During the treatment period, ECG...” |
| Description of change | Clarifying that ECG assessments after Visit 26 are every 16 weeks (instead of indicating every 2nd imaging). |
| Rationale for change | Administrative (clarification) |
| | |
| Section to be changed | Flow Charts; LVEF including footnote Section 3.3.3; Exclusion criterion No. 14 Section 5.2.4.4; Left Ventricular Ejection Fraction |
| Description of change | Eligibility criterion for LVEF and post-baseline LVEF assessments removed. |

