| Rationale for change | LVEF monitoring was initially included in the protocol to investigate potential effects of afatinib on the myocardium as are seen with other HER2 inhibitors. Sponsor has over the years collected extensive clinical data of patients treated with afatinib, which allows us to dismiss this as a potential ADR related to afatinib. It is therefore considered adequate to remove this type of assessment throughout the study. |
| | |
| Section to be changed | Flow Charts; HRQOL footnote Section 5.1.2.3 Health-related quality of life Section 6.2.2 Treatment period |
| Description of change | Collection of questionnaires for assessment of HRQOL will stop after database lock for primary analysis. Sentence to address this is added to applicable Flow Chart footnotes and Sections. |
| Rationale for change | Primary analysis will include all analysis, including analysis of HRQOL data. Therefore continued collection is not considered to add additional value once the database lock for the primary analysis is complete. |
| | |
| Section to be changed | Flow Charts; Below tables (item OP) and footnote |
| Description of change | Frequency of contacts in the Observational Period will be every 3 months instead of every 4 weeks after database lock for primary analysis. |
| Rationale for change | Primary analysis will include all analysis and therefore less frequent collection of data is considered adequate. |
| | |
| Section to be changed | Abbreviations |
| Description of change | Addition: REP – Residual effect period |
| Rationale for change | Administrative |

Proprietary confidential information. © 2019 Boehringer Ingelheim International GmbH or one or more of its affiliated companies

| | |
|------------------------------|---|
| Section to be changed | Section 3.1 Overall trial design and plan |
| Description of change | Deletion: For details on treatment beyond progression, see Section 3.2. |
| Rationale for change | Administrative, should have been removed with previous amendment. |
| Section to be changed | Section 3.1 Overall trial design and plan |
| Description of change | Addition at end of 8 th paragraph (Primary statistical analysis...): An addendum to the clinical trial report may be used to summarise data collected beyond database lock for the primary analysis. |
| Rationale for change | Clarification on reporting of data. |

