7. PLANNED ANALYSIS

The primary analysis for the primary endpoint, PFS, will take place after the number of required events have occurred based on independent review. Final analyses will be done after final database lock.

For display purpose, in the End-of-Text tables, the set of summary statistics is: N / Mean / StD / Min / Median / Max for continuous variables. Tabulations of frequencies for categorical data will include all possible categories and will display the number of observations in a category as well as the percentage (%) relative to the respective treatment group (unless otherwise specified, all patients in the respective patient set whether they have non-missing values or not). Percentages will be rounded to one decimal place. The category missing will be displayed only if there are actually missing values.

An independent data monitoring committee (DMC) will oversee the trial conduct and review safety data according to DMC SAP [3].

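### LVEF is still a listed safety measure and a planned SAP table although the schedule no longer measures it, and any LVEF event percentage would by default include unmeasured patients in its denominator

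*SAP*

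**What the plan says.** Two current passages keep LVEF in the analysis.

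- Protocol 7.3.3 (Safety analyses) includes among its key safety measures "decreased cardiac left ventricular function (reduction to below LLN and" a drop of at least 20% relative to baseline.
- SAP 7.8.3 (Vital signs) says "A summary table of left ventricular ejection fraction (LVEF) will be produced for the final and minimum on-treatment values", with percentage change from baseline, and adds: "The number of patients with a significant LVEF event will also be presented".

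The current measurement plan has no LVEF. Neither flow chart has an LVEF row. Besides adverse events, the synopsis safety criteria cover "changes in safety laboratory parameters, vital signs, ECOG status and ECG". Protocol 5.2.4.5 defines the vital signs section as "Vital signs (blood pressure and pulse after 5 minutes seated rest), and body weight". The safety endpoints in protocol 5.2.1 and the other assessments in 5.2.4 do not mention LVEF either.

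The log for Amendment 3 (28 March 2017) explains why: "Eligibility criterion for LVEF and post-baseline LVEF assessments removed", with the reason ending "It is therefore considered adequate to remove this type of assessment throughout the study". The SAP has a single version, dated 1 April 2016, about a year before that amendment.

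On denominators, SAP section 7 says that categorical tabulations show a count and a percentage. Unless otherwise specified, the percentage is taken over "all patients in the respective patient set whether they have non-missing values or not". SAP 7.8 places all safety analyses on the treated set, and 7.8.3 gives no LVEF-specific denominator.

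**The concern.** A significant LVEF event is defined by a fall from baseline, so it can be seen only in a patient who has both a baseline and an on-treatment value. Patients enrolled after LVEF was dropped have neither under the current schedule. Patients who were on treatment at that time may have a truncated series. The plan does not say who belongs in the LVEF table.

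If the event count is turned into a percentage under the section 7 default, every unmeasured patient is in effect counted as event-free. The printed percentage then depends on how many patients happened to be enrolled before the change as well as on the drug. Even a bare count is hard to read without the number assessed beside it. What is at stake is the accuracy of one cardiac safety figure in the trial report. The primary analysis and the formal hypothesis are not touched.

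**Working it through.** **The plan's own figure.** The documents state no LVEF event rate, number assessed or LVEF sample size, so there is nothing to reproduce.

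**Step 1: do the current texts conflict?** Protocol 7.3.3 and SAP 7.8.3 require LVEF. The flow charts, synopsis, 5.2.1 and 5.2.4 do not collect it. The conflict lies between current passages; the amendment log is used only to date the cause.

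**Step 2: effect of the denominator.** Let f = assessed / treated, where assessed means a baseline and at least one on-treatment LVEF.

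Printed % = events / treated = f × (events / assessed).

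With at least one event and f < 1, the printed figure is below the rate among assessed patients by the factor f.

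With assumed rates among assessed patients, for illustration only:

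| f (assumed) | true 2% prints as | true 5% prints as |
|---|---|---|
| 0.90 | 1.8% | 4.5% |
| 0.75 | 1.5% | 3.75% |
| 0.50 | 1.0% | 2.5% |
| 0.25 | 0.5% | 1.25% |

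As a count: suppose 4 events among the 220 patients planned for afatinib. The all-patients denominator gives 4/220 = 1.8% however many were measured. On assessed patients it is 4/165 = 2.4%, 4/110 = 3.6% or 4/55 = 7.3%.

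**Step 3: what can be said about f.** Inputs:

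- LVEF removed on 28 March 2017 (Amendment 3 date; assumes immediate implementation).
- Last patient randomised about 10 February 2018. This is inferred: Amendment 4 refers to 10 February 2019 in the context of one year after last randomisation.
- Interval between the two: about 10.5 months.
- Total randomised: 330.
- Accrual: protocol 7.6 gives 9.5 per month in the text and 12.5 in the table footnote. Both are planning values, not observed ones. As a slower alternative, average accrual from the protocol date (7 February 2013) over about 60 months is 330 / 60 = 5.5 per month.

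Randomised after the amendment = 10.5 × monthly rate:

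| Rate per month | Patients after removal | Share of 330 | f at most |
|---|---|---|---|
| 5.5 | about 58 | 18% | 0.82 |
| 9.5 | about 100 | 30% | 0.70 |
| 12.5 | about 131 | 40% | 0.60 |

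These ceilings on f treat the randomised and treated sets as nearly equal. Amendment 3 needed local ethics and authority approval before implementation. Later approval would leave fewer patients unmeasured and raise the ceilings. Earlier patients with no on-treatment LVEF would push f below them.

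**Step 4: between-arm comparison.** The loss follows calendar date, so under concurrent randomisation f should be similar in both arms. The ratio of rates is then roughly preserved, while the absolute rates and the risk difference both shrink by f.

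**The case against.** The strongest reply is that this is version lag with little consequence, and much of it stands.

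- SAP 7.8.3 promises a number of patients, not a rate. The percentage enters only through the general rule in section 7, which is a plausible reading but not an explicit instruction for this table.
- The same part of section 7 requires N for continuous variables, so the summary of final and minimum LVEF would show how many patients were measured. It also requires a missing category when values are missing. A careful reader could recompute the rate.
- The event definition already implies patients with a baseline and an on-treatment value.
- The analysis is descriptive. LVEF feeds no hypothesis, efficacy endpoint or stopping rule, and adverse events continue to be collected in all treated patients.

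A reader might infer that following the SAP is bound to yield a cardiac event rate about 30–40% too low. The documents do not support that. It needs a percentage to be printed, at least one event, accrual at the planned rate and immediate implementation. Planned accrual also fits the dates poorly: 330 patients at 9.5 to 12.5 per month, counted back from February 2018, would put the first patient in about March to November 2015, although the protocol is dated February 2013. A reader might equally infer that the table would be empty. That is not supported either, because patients treated before the change may have valid data.

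What the reply does not remove is that the table's population is undefined and that the stated default denominator is the wrong one for a measure that stopped being collected.

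**Conclusion.** The point holds at low severity. The current protocol and SAP keep an LVEF measure that the current schedule does not collect. Under the SAP's stated default, any LVEF event percentage would be diluted by the factor f.

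The size cannot be fixed from the documents. On the dates and accrual assumptions above, about 18% to 40% of patients were randomised after the removal, which caps f at about 0.82 to 0.60. An assumed 5% rate among assessed patients would then print as at most about 4.1% (5% × 0.82) to 3.0% (5% × 0.60). Delayed local approval would narrow the gap, and missing on-treatment values would widen it.

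The effect is confined to one descriptive safety display. The gap would be visible from the N and the missing category, and the ratio between arms is roughly kept.

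**What to change.** In SAP 7.8.3, limit the LVEF table and any event percentage to treated patients with a baseline and at least one on-treatment LVEF. Show that N per arm as the denominator, and state that LVEF collection stopped during the trial.

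In protocol 7.3.3, reconcile the list with the schedule: either remove the LVEF measure or limit it to those patients.

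The cost is a sentence or two in each document. No new data are needed and no other analysis changes.

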7.8.4 ECG

Not applicable as ECG measurement data are not collected in this study.

7.8.5 Others

Pharmacokinetic analyses (i.e. of afatinib pre- and post-dose plasma concentrations) will be performed according to Section 7.3.6 of the CTP.

10. HISTORY TABLE

Table 10: 1 History table

| Version | Date (DD-MMM-YY) | Author | Sections changed | Brief description of change |
|---------|------------------|------------|------------------|--|
| Final | 01-APR-16 | [REDACTED] | None | This is the final TSAP without any modification. |
